## **4. STUDY DESIGN AND PLAN**

This is a Phase 2, double-blind, randomized, placebo-controlled, multicenter study, evaluating the effects of OCA, and the subsequent addition of statin therapy, on lipoprotein metabolism in subjects with NASH with fibrosis stage 1 to 4, but no evidence of hepatic decompensation, in the DB phase, followed by an open-label LTSE phase to evaluate long term safety and efficacy.

Approximately 80 subjects with histological evidence of definite or probable NASH, who meet all inclusion and none of the exclusion criteria will be enrolled in the study. The histological evidence of definite or probable NASH will be based on the central read of a liver biopsy obtained no more than 1 year prior to randomization and a nonalcoholic fatty liver disease activity score (NAS) of 4 or greater. Subjects not using statin therapy (ie, statin-free) and statin-treated subjects may be enrolled. Statin-treated subjects will be required to stop statin treatment (after signing informed consent) for up to 5 weeks, including a 4-week statin washout period, prior to Randomization/Day 1.

Subjects will have a screening period of up to 5 weeks prior to Randomization/Day 1. At the Randomization (Day 1) Visit, subjects will be randomized in a 1:1:1:1 ratio to receive OCA 5 mg, OCA 10 mg, OCA 25 mg, or placebo, orally, once daily, for 16 weeks. Randomization will be stratified by the pre-randomization fasting serum LDLc ( $\leq$ 125 mg/dL or  $>$ 125 mg/dL) and baseline fibrosis stage (stage 1, 2 or stage 3, 4).

[figure not shown]
Subjects will attend on-site clinic visits at Weeks 2, 4, 8, 12, and 16 and will be contacted at Weeks 6, 10 and 14 to assess safety and treatment compliance. At the Week 4 Visit, all subjects will initiate treatment with atorvastatin at a dose of 10 mg once daily. At the Week 8 Visit, atorvastatin will be increased to 20 mg once daily (if 10 mg daily is tolerated), and continued for an additional 4 weeks. After 4 weeks of treatment at 20 mg, the atorvastatin dose may be titrated (up or down) as clinically indicated. The final visit during the DB phase will occur at Week 16, after which subjects may continue into the open-label LTSE.

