## 11. SAFETY ANALYSES

All safety analyses will be based on the Safety Population. The AE, vital signs, clinical laboratory evaluations, and ECG analyses are defined as secondary endpoints per the protocol. The anthropometric measures, blood pressure, and cardiovascular risk scores are defined as exploratory efficacy endpoints per the protocol.

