### **11.3.1. Pruritus**

Treatment-emergent pruritus, defined as any preferred term that contains “*Prur*,” will be summarized separately by the MedDRA SOC, treatment group, and PT as a subset of all TEAEs.

An analysis of treatment-emergent pruritus event days per subject years on study will be performed. The days at each severity grade, including the total days of event, and the percent of event days on study at each severity grade, including the total, will be summarized.

In order to explore the relationship between pruritus and the investigational product, the following time-to-event analyses will be performed:

- Total duration of treatment-emergent pruritus
  - Duration of each treatment-emergent pruritus event will be calculated as end date – start date +1. For events that are ongoing at Week 16, the Week 16 date will be used as the end date. The sum of each event will be summed for an overall by-patient duration during the DB phase.
- Time to first onset of treatment-emergent pruritus
  - The time to the start of the first episode will be calculated by date of onset of first episode – date of first dose of investigational product + 1.
  - Subjects who never report an AE of pruritus will be censored at the date of completion or discontinuation.
- Time to onset of the most severe treatment-emergent pruritus
  - The time to the start of the most severe pruritus will be calculated by date of onset of the most severe pruritus – date of first dose of investigational product + 1.
  - Subjects who never report a severe AE of pruritus will be censored at the date of study completion or discontinuation.
- Time to resolution of the most severe treatment-emergent pruritus event
  - The time to resolution of the most severe event of treatment-emergent pruritus will be calculated by date of resolution of the most severe event of treatment-emergent pruritus – start date of the most severe event of treatment-emergent pruritus + 1.
  - Subjects whose most severe event of treatment-emergent pruritus is ongoing will be censored at the date of study completion or discontinuation. For subjects that are lost to follow-up, the last contact date will be used.
  - Only subjects that report a pruritus event are included in this analysis.

- For subjects reporting multiple events at the most severe level, the event with the longest duration will be used.
- Separate summaries will be presented for those who discontinue due to pruritus.

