The analysis of time-to-event will include the number of subjects with the event (first onset, most severe), the number of subjects without the event (censored), descriptive statistics of total duration of pruritus, descriptive statistics of time for those with an event, and range in days for all subjects. Kaplan-Meier (KM) estimates will be calculated by treatment group. The quartiles, including the median time-to-event and their respective 2-sided 95% CIs, will be presented. KM estimates will be plotted as a “survival curve” for each treatment group, with the number at risk identified. The comparison of OCA to placebo will be summarized using a log-rank test stratified by randomization strata factors.

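### Time to pruritus resolution is tested OCA versus placebo only among subjects who report pruritus, a comparison that randomisation does not protect

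*SAP*

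**What the plan says.** SAP Section 11.3.1 introduces its list with "In order to explore the relationship between pruritus and the investigational product, the following time-to-event analyses will be performed". The list has four items: total duration, time to first onset, time to onset of the most severe pruritus, and time to resolution of the most severe event. For resolution it adds three rules:

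- Analysis set: "Only subjects that report a pruritus event are included in this analysis".
- Censoring: "Subjects whose most severe event of treatment-emergent pruritus is ongoing will be censored at the date of study completion or discontinuation".
- Choice of event: "For subjects reporting multiple events at the most severe level, the event with the longest duration will be used".

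The section then prescribes Kaplan-Meier estimates by treatment group and ends: "The comparison of OCA to placebo will be summarized using a log-rank test stratified by randomization strata factors". Nothing exempts resolution from that sentence, and nothing labels the resolution comparison as non-randomised. Appendix A gives resolution its own table (14.3.1.14.5) beside the two onset tables.

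Three other places matter. Section 11 sets the general rule: "All safety analyses will be based on the Safety Population". Section 11.3 names pruritus as an adverse event of special interest. Section 6.2.8 makes all confidence intervals and p-values descriptive. Section 11.3.1 also plans an analysis of pruritus event days relative to time on study (Table 14.3.1.14.6), which it does not expressly limit to subjects with pruritus.

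**The concern.** The two onset analyses keep every Safety Population subject and censor those without the event, so the randomised groups stay intact. Resolution is different. Its analysis set is defined by something that happens after randomisation and that the drug may influence. If OCA produces pruritus in subjects who would not otherwise have had it, the OCA reporters are a mixture of background and added cases, while the placebo reporters are background cases only. A difference in resolution time between them can then reflect the mixture and not any change in how long a given subject itches. This holds even with one event per subject, so it is separate from the longest-event rule.

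At stake is the safety description of an adverse event of special interest. A drug that only adds short-lived itch could be described as having pruritus that resolves faster than on placebo. A drug that adds long-lived itch would show incidence and persistence mixed together.

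**Working it through.** **Plan figures.** The SAP states no incidence, duration or power for pruritus, so there is nothing of its own to reproduce here. Its one design figure, 97.3% power for LDLc in Section 5, is matched by a one-sample t-test (n = 20, 22/24: 0.9729) and has no bearing on this point.

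**Inputs from the SAP (Section 4).** "Approximately 80 subjects with histological evidence of definite or probable NASH", and "subjects will be randomized in a 1:1:1:1 ratio to receive OCA 5 mg, OCA 10 mg, OCA 25 mg, or placebo". That gives about 20 per arm: 60 vs 20 if OCA is pooled, 20 vs 20 for a single dose. The log-rank has 2 × 2 = 4 strata and follow-up is 16 × 7 = 112 days.

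**Assumptions (not in the SAP).** Background pruritus has the same incidence and duration in both arms. OCA adds further cases and changes nobody's duration. Durations are exponential, onset is uniform over roughly the first 84 days, and censoring is at day 112.

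**Why the curves separate.** With median m, the fraction still itching t days after onset is 2^(−t/m). Take 20% background at a median of 60 days and 35% added on OCA at a median of 14 days, pooled OCA 60 vs placebo 20:

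- Placebo reporters: 20 × 0.20 = 4. Still itching at day 28: 2^(−28/60) = 0.72.
- OCA reporters: 60 × 0.20 = 12 background plus 60 × 0.35 = 21 added, total 33. Still itching at day 28: (12 × 0.72 + 21 × 2^(−28/14)) / 33 = (8.7 + 5.25) / 33 = 0.42.

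So 42% of OCA reporters against 72% of placebo reporters still itch, with no effect on any subject's duration. Yet mean itch per randomised subject (mean = m / ln 2, ignoring truncation at day 112) is higher on OCA: 0.20 × 86.6 = 17.3 days on placebo and 17.3 + 0.35 × 20.2 = 24.4 days on OCA. If the two medians are equal, the two curves coincide.

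**Rejection in favour of OCA** (nominal 2.5%; 60 vs 20; stratified log-rank; 35% added by OCA unless stated):

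| Background incidence | Median, background / added (days) | Rejection |
|---|---|---|
| 20% | 30 / 30 | 1.1% |
| 20% | 30 / 21 | 3.0% |
| 5% | 60 / 14 | 4.6% |
| 10% | 60 / 14 | 9.6% |
| 20% | 60 / 14 | 15-16% |
| 25% (more extreme setting) | 90 / 10 | 25-26% (unstratified 26-27%) |

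For 20 vs 20, the last two rows give 11-12% and 18-21% stratified.

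**Total rejection, both directions** (nominal 5%; 60 vs 20; stratified; pruritus 40% on OCA, 10% on placebo):

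| Median, background / added (days) | Rejection |
|---|---|
| 30 / 30 | 8% |
| 14 / 42 | 20% |
| 10 / 60 | 31% |
| 42 / 14 | 8% |
| 60 / 10 | 12% |

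The fair reference is the equal-duration 8%, which is small-sample behaviour. The excess with longer added itch is therefore about 20 − 8 = 12 and 31 − 8 = 23 percentage points. Over incidences from 25%/5% to 50%/20% with unequal durations, the stratified range is 4-35%. For 20 vs 20 it is 0.5-20%, because sparse strata make the test conservative.

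**Bias or noise.** At ten times the sample (600 vs 200), rejection rises to 47-100% with unequal durations and stays at 5-7% with equal ones. The excess is selection, and it grows with sample size.

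**The case against.** Several points on the other side have weight.

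- **Coverage of the log-rank sentence is inferred.** The event counts in that paragraph name only first onset and most severe. The list also contains total duration, which has no event or censoring rule and cannot take a log-rank test, so the sentence cannot apply literally to every item. Still, the parenthesis qualifies the counts and not the test, and resolution is listed as a time-to-event analysis with its own censoring rule. Inclusion is the natural reading but not a certain one.
- **The size depends on the inputs.** The larger figures in favour of OCA need background itch lasting four to nine times as long as added itch, and 20-25% background incidence. With similar durations the test is near nominal in that direction. This stands.
- **Little rides on the p-value.** Section 6.2.8 makes it descriptive, and 5-20% incidence in 20 placebo subjects gives only 1-4 placebo cases. This stands too, and sets the severity. Descriptive status does not, however, make the two groups comparable.
- **All-subject outputs are already planned.** Time to first onset and event days relative to time on study would sit beside the resolution result and reveal added itching. They reduce the risk of misreading, but do not tell a reader that the resolution test is unprotected.

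A reader might infer that the resolution p-value is biased whenever OCA changes who itches, or that it says nothing about OCA. The documents do not support that. Unequal durations are also needed, the SAP gives none, and resolution among cases remains a legitimate description. Nor do they support inferring a false confirmatory claim.

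**Conclusion.** The point holds in limited form. As most naturally read, Section 11.3.1 tests OCA against placebo on resolution in a set selected by a post-randomisation outcome. The test can mislead if two conditions both hold: OCA changes who gets pruritus, and the added cases differ in duration from background cases. It can then err in either direction. Under assumed incidences and durations the distortion runs from none (equal or similar durations) to about 27% rejection in favour of OCA against 2.5% nominal, or about 20-31% total rejection where added itch is longer, against about 8% with equal durations. None of these rates can be narrowed from the SAP. The harm is a misleading description of a safety finding; no primary or confirmatory conclusion is touched. Severity: minor.

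**What to change.** In Section 11.3.1:

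1. Keep the Kaplan-Meier curves and quartiles for time to resolution as a description within pruritus cases, and label the comparison between groups as non-randomised.
2. State that the log-rank comparison applies to the two onset analyses and not to resolution. This also settles the ambiguity about its scope.
3. Make the OCA-placebo comparison of pruritus burden on the measure the section already plans, event days relative to time on study. Include all Safety Population subjects, counting 0 for those without pruritus, and give the difference with a 95% CI.

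Raw total pruritus days should not carry this comparison. They shrink when a subject leaves early, and the section itself expects some discontinuations due to pruritus, so more drop-out on OCA would flatter OCA.

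Cost: wording in one section, one exploratory p-value lost, and one comparison added on data already derived. No new data are needed.

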### **11.3.2. Hepatic Disorders**

Hepatic disorders are defined as events included in the Hepatic Disorders Standardized MedDRA query (SMQ), excluding the following sub-SMQs: Congenital, familial, neonatal and genetic disorders of the liver; Hepatitis, non-infectious; Liver infections; and Pregnancy-related hepatic disorders. See [Appendix B](#) for a list of the preferred terms and their associated codes.

### **11.3.3. Dyslipidaemia**

AE lipid profile changes, defined in the Dyslipidaemia SMQ, will be reported. See [Appendix C](#) for a list of the preferred terms and their associated codes.

### **11.3.4. Myopathy**

Myopathy is defined as any condition in the Rhabdomyolysis and Myopathy SMQs. See [Appendix D](#) for a list of the preferred terms and their associated codes.

## **11.4. Adjudicated Cardiovascular Events**

All suspected cardiovascular events that occur after administration of the first dose of investigational product will be reviewed and adjudicated by the Cardiovascular Adjudication Committee according to criteria defined in their charter. Events adjudicated by the committee will be included in the cardiovascular event analysis.

Summaries that are displayed by system organ class and preferred terms will be ordered by descending order of incidence, for all OCA-treated patients, of system organ class and by preferred terms within each system organ class. All summaries of incidence will include the associated exact binomial 95% CI. Summaries of the following types will be presented by treatment group:

- Subject incidence of adjudicated cardiovascular events and the total number of entries by MedDRA system organ class and preferred term

In order to explore the relationship between adjudicated cardiovascular events and the investigational product, the following time-to-event analyses will be performed:

- Time to first onset of adjudicated cardiovascular event

- The time to the start of the first event will be calculated by date of onset of first event – date of first dose of investigational product + 1.
- Subjects without adjudicated events will be censored at the date of completion or early termination.
- Time to onset of most severe adjudicated cardiovascular event
  - The time to the onset of most severe event will be calculated by date of onset of most severe event – date of first dose of investigational product + 1.
  - Subjects without adjudicated events will be censored at the date of completion or early termination.

The incidence and time-to-event analysis for adjudicated cardiovascular events will be repeated for suspected cardiovascular events.

## **11.5. On-Study Medical or Surgical Procedures**

On-study medical or surgical procedure data will be collected from the time that signed informed consent is obtained until the subject fully completes her/his study participation of the study. Verbatim procedure terms on eCRFs will be mapped to preferred terms and system organ classes using MedDRA (version 18.1).

All on-study medical or surgical procedure data will be presented in a by-subject data listing.

## **11.6. Clinical Laboratory Evaluations**

Clinical laboratory evaluations during the DB are assessed at the central laboratory. The central laboratory reference/normal ranges will be used in determining whether a subject's value is above (H) or below (L) the reference/normal range. A listing of available laboratory reference/normal ranges for each laboratory parameter will be provided including age, sex, and values with units.

Quantitative hematology, coagulation, and serum chemistry laboratory parameters will be summarized by treatment group in SI and conventional units using arithmetic summary statistics as described in [Section 6.2.1](#) at Baseline and at each scheduled DB post-Baseline visit. Change from Baseline will also be summarized in the same manner. Re-tests or unscheduled visit results after first dose of investigational product in the DB will not be summarized but will be included in the data listings. Re-tests or unscheduled visit results prior to the administration time of the first dose in the DB will be included in the calculation of Baseline.

For laboratory test results that are below the quantifiable limits:

    Imputed laboratory result = (numeric portion of the result)  $\times$  0.9.

For laboratory test results that are above the quantifiable limits:

    Imputed laboratory result = (numeric portion of the result)  $\times$  1.1.

In addition, shift tables (ie, low-normal-high at Baseline versus low-normal-high at DB post-Baseline visit in a 3-by-3 contingency table) from Baseline to worst value, last value, and at each

scheduled DB post-Baseline visit will be provided for hematology, coagulation, and serum chemistry by treatment group. Worst post-Baseline value is defined as the most abnormal value.

Urinalysis results will not be summarized but will be provided in a data listing.

Listings of all laboratory values will flag values outside of the normal range as high (H) or low (L) and indicate whether or not a value is clinically significant (CS), based on Investigator judgment.

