##### **3.2.3. Safety and Tolerability Endpoints**

The DB safety and tolerability endpoints include the following:

- Extent of exposure to OCA and Atorvastatin

- Incidence of Treatment-Emergent adverse events (TEAEs)
- Observed values and change from Baseline at each DB post-Baseline visit in quantitative clinical laboratory values for coagulation, hematology, and serum chemistry
- Shift tables (ie, low-normal-high at Baseline versus low-normal-high at each DB post-Baseline visit in a 3-by-3 contingency table) from Baseline to worst DB post-Baseline value, last DB post-Baseline value, and at each scheduled DB post-Baseline visit for quantitative hematology, coagulation, and serum chemistry
- Observed values and change from Baseline at each DB post-Baseline visit in vital signs (ie, body temperature, sitting heart rate, and respiratory rate). Note: blood pressure (sitting) is described below in [Section 3.3.6](#)
- Observed values at Baseline and each DB post-Baseline visit, and change from Baseline at each DB post-Baseline visit in electrocardiogram (ECG) parameters (time between 2 consecutive R waves [RR], heart rate, PR, QRS, the time from the start of the Q wave an T wave (in heart's electrical cycle) (QT), QT interval corrected by Bazett's formula (QTcB), and QT interval corrected by Fridericia's formula (QTcF))
- Categorical summaries of abnormal QTcF values (ie, > 450 msec, > 480 msec, and > 500 msec) and change from baseline values (> 30 msec and > 60 msec)

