#### 3.3.1. Liver Biochemistry and Markers of Liver Function

For the laboratory parameters albumin, alkaline phosphatase (ALP (isoenzymes)), ALT (isoenzymes), AST, total and direct bilirubin, gamma-glutamyl transferase (GGT), and INR (International Normalized Ratio), and platelets:

- Observed values, change from Baseline, and percentage change from Baseline at each DB post-Baseline visit
- Shift from Baseline to each DB post-Baseline visit

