## 6. GENERAL ANALYSIS CONSIDERATIONS

### 6.1. Data Reporting

The statistical analyses will be reported using summary tables, figures, and data listings. All output will be incorporated into Microsoft Word rich text format (.rtf) files, sorted and labeled according to the ICH recommendations, and formatted to the appropriate page size(s).

Laboratory units will be summarized and presented in the International System of Units (SI) and conventional units.

Individual subject data obtained from the electronic case report forms (eCRFs), external laboratory data, and any derived data (such as change from Baseline and percent change from Baseline) will be presented in data listings by subject. Data from all assessments, whether scheduled or unscheduled, will be listed by subject and visit. Unscheduled visits and visits occurring more than one day outside protocol defined window will not be included in the table summaries, excluding transient elastography measurements

The analyses described in this plan are considered a priori, in that they have been defined prior to database lock of the DB. Post hoc analyses will be labeled as such on the outputs and identified in the CSR.

Analyses and tabulations will be performed using SAS® Version 9.3 or higher. PK parameters will be estimated using Phoenix® WinNonlin® Version 6.3 or higher. The following processes will be employed to validate statistical outputs: analysis datasets, summary tables, and data listings will be verified through independent programming; graphical displays will be compared against supporting summary tables; and all outputs will undergo a senior-level statistical review. The process includes confirmation that statistically valid methods have been implemented and that all data manipulations and calculations are appropriate and accurate. Checks will be made to ensure accuracy, adherence to this SAP, consistency within tables, and agreement between tables and their corresponding data listings. Upon completion of validation/verification and quality review procedures, all documentation will be collected and filed in the study master file by the project statistician or designee.

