#### 6.2.1. Arithmetic Summaries

Continuous variables will be summarized with means, standard deviations (SDs), standard errors (SEMs) of the mean, medians, interquartile ranges (IQRs), minimums, and maximums.

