## **9.3. Exploratory Efficacy Analyses**

### **9.3.1. Liver Biochemistry and Markers of Liver Function**

The following laboratory parameters will be summarized by treatment group: albumin, ALP, ALT (isoenzymes), AST, direct bilirubin, GGT, INR, total bilirubin, and platelets.

Analyses of observed laboratory values will be carried out using a repeated measures ANCOVA model with change from Baseline as the dependent variable, including treatment group, and randomization stratification factors as fixed effects and Baseline as a covariate as described in [Section 6.2.3](#). The same analysis will be carried out using percentage change from Baseline as the dependent variable.

Arithmetic summary statistics as described in [Section 6.2.1](#) will be used to summarize the laboratory values by treatment group and visit. The results, change from baseline, and percentage change from baseline, as well as estimates of LS means, SEs, and 95% CIs, will be presented by treatment group. Estimates of the mean difference between each active treatment group and placebo group, the SE of the difference, and 95% CI of the difference will be presented.

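### Laboratory shift tables stop at low/normal/high, so for ALT, AST, ALP, GGT and total bilirubin a subject above ULN at Baseline cannot show worsening, and no listed laboratory table counts marked rises by arm

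*SAP*

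**What the plan says.** SAP section 3.2.3 defines the laboratory shift endpoint as "low-normal-high at Baseline versus low-normal-high at each DB post-Baseline visit in a 3-by-3 contingency table", applied to the worst value, the last value and each scheduled visit. Section 11.6 repeats this as "low-normal-high at Baseline versus low-normal-high at DB post-Baseline visit in a 3-by-3 contingency table" and takes high and low only from the central laboratory reference range. It adds that "Worst post-Baseline value is defined as the most abnormal value".

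Two rules limit which samples enter tables. Section 11.6 states that "Re-tests or unscheduled visit results after first dose of investigational product in the DB will not be summarized". Section 6.1 states that "Unscheduled visits and visits occurring more than one day outside protocol defined window will not be included in the table summaries", with transient elastography as the only exception.

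For liver biochemistry, section 3.3.1 also lists "Shift from Baseline to each DB post-Baseline visit". The matching analysis section, 9.3.1, presents "The results, change from baseline, and percentage change from baseline, as well as estimates of LS means, SEs, and 95% CIs" and differences from placebo, but no shift.

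The safety laboratory tables in Appendix A (14.3.4.1.1 to 14.3.4.4.2) are summaries and shift analyses only. Table 14.2.7, liver biochemistry, is in the EE Population.

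**The concern.** Trial subjects have biopsy-confirmed NASH with fibrosis stage 1 to 4. Section 8.3 itself plans a Baseline class above ULN for ALT, AST and bilirubin, so the SAP provides for subjects who start high. Section 11.3 makes hepatic disorders an adverse event of special interest. Yet for those subjects the shift tables cannot separate a stable value from a many-fold rise, and for subjects who start normal, slight and large rises share one cell.

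At stake is a basic safety count: how many subjects per arm had a marked rise in a liver test, judged from the laboratory values. Section 11.8 does give such counts for QTcF, at three absolute and two change thresholds. Nothing comparable is listed for liver tests.

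The sample rules add a second loss. A sharp rise may be found or confirmed at an unscheduled visit, and that value does not reach the worst-value shift.

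**Working it through.** The SAP states no figure on this point, so there is none to reproduce. The check applies the shift rule to values and then asks what the other outputs would show.

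**1. The rule itself.** Set ULN = 1. Take assumed Baselines of 1.1, 1.5, 2 and 3 x ULN and multiply each by 1, 2, 3, 5 and 10. All 4 x 5 = 20 combinations fall in high-to-high. A subject unchanged at 1.5 x ULN and one rising from 1.5 to 15 x ULN give the same entry.

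**2. Subjects affected.** The design has 20 per arm, about 80 in all (sections 4 and 5). The share above ULN at Baseline is not given, so a range is used: 20 x 0.10 = 2, 20 x 0.50 = 10 and 20 x 0.90 = 18 per arm, for each test. At 10% the total is 80 x 0.10 = 8.

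**3. Whether the by-visit summaries fill the gap.** Section 6.2.1 gives mean, SD, SEM, "medians, interquartile ranges (IQRs), minimums, and maximums". Assumed values: ULN between 41 and 60 U/L; all 20 subjects in an arm start at ALT 70 (70/60 = 1.17 to 70/41 = 1.71 x ULN); chemistry is drawn at Weeks 2, 4, 8, 12 and 16.

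- Case A: one subject is at 400 at Weeks 8, 12 and 16; all other values are 65.
- Case B: three subjects are each at 400 at a different one of those visits; all other values are 65.

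In both cases, each of Weeks 8, 12 and 16 has one change of +330 and 19 of -5:

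- mean = (330 - 19 x 5)/20 = 11.75
- SD = sqrt((318.25² + 19 x 16.75²)/19) = sqrt(106613.75/19) = 74.9
- median -5, minimum -5, maximum +330

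At Weeks 2 and 4 every change is -5. The value 65 is still high (65/60 = 1.08 to 65/41 = 1.59 x ULN), so the worst, last and every by-visit shift is 20 of 20 high-to-high in both cases. The tables are identical, but the number of subjects at 400/70 = 5.7 x Baseline is 1 (5%) in A and 3 (15%) in B.

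**4. Sample rules.** A subject who is normal at Baseline and at every scheduled visit, with 400 U/L at one unscheduled visit, enters the worst-value shift as normal-to-normal. Section 11.6 does let unscheduled results before the first dose enter Baseline, so the exclusion applies only after dosing.

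**5. Proposed counts on the same cases.** 400 U/L is 400/60 = 6.67 to 400/41 = 9.76 x ULN. With Baseline above ULN, the band above 5 x ULN shows 1/20 in A and 3/20 in B, as do the counts at 2 x and 3 x Baseline. A subject stable at 2 x ULN is not counted as a rise. A rise from 1.2 to 2.9 x ULN stays at or below 3 x ULN but is 2.9/1.2 = 2.4 x Baseline, so the Baseline multiple counts it. Bilirubin going from 0.3 to 0.6 mg/dL is 2 x Baseline but below an assumed ULN of 1.0 to 1.2, so requiring a value above ULN leaves it out.

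**The case against.** The 3-by-3 shift is stated consistently, and marked rises are not invisible. By-visit Safety Population summaries include the maximum. Section 9.3.1 adds percentage change and differences from placebo. Hepatic terms such as raised ALT are tabulated by arm with time to onset, and section 11.2 adds maximum severity and an analysis up to Week 4. Every value is listed with flags. With 20 per arm a count could be read from the listings, and labelled post hoc output is allowed. Cases A and B were also built to coincide.

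Much of this stands. A reader might infer that the plan hides liver injury altogether; it does not. But none of these outputs is a by-arm count from laboratory values. The maximum shows that a peak occurred, not in how many subjects. Table 14.2.7 uses the EE Population, which section 7.4 limits to subjects completing at the indicated doses. The event tables depend on investigators reporting a rise as an adverse event. The listings contain no counts. Cases A and B show that the loss is possible, not that it is likely.

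Four stronger readings are not supported:

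- That every liver test is affected in this way. Albumin and platelets worsen downward, so a high Baseline can still show worsening.
- That the worst-value shift is the only table counting subjects. The last-value and by-visit shifts do so too, with the same limit.
- That it is undefined which samples feed the worst value. Sections 6.1 and 11.6 read together exclude unscheduled results; the fault is what that rule drops.
- That the section 3.3.1 shift has no usable categories. It can take those of section 11.6.

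**Conclusion.** The point holds for ALT, AST, ALP, GGT and total bilirubin. The shift tables cannot show worsening in a subject above ULN at Baseline, no listed laboratory table gives a by-arm count of marked rises, and the sample rules drop unscheduled, re-test and out-of-window peaks from the worst-value shift. This follows from the stated categories and table list, and needs no assumption.

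The size does rest on assumption: 2 to 18 of 20 subjects per arm for a Baseline share of 10% to 90%, and 1 versus 3 indistinguishable subjects in a constructed example. The effect is on safety reporting only; no primary result changes. It is worth correcting before database lock because the data are already collected.

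**What to change.** Keep the 3-by-3 shifts. Add to section 11.6 and Appendix A one Safety Population table by treatment group of each subject's highest double-blind post-Baseline ALT, AST, ALP, GGT and total bilirubin. State that re-test, unscheduled and out-of-window results count, as an exception to sections 6.1 and 11.6. Show number and percentage of subjects:

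- (a) in a few fixed bands of ULN, split by Baseline at or below versus above ULN. For example: ALT and AST up to 3, above 3 to 5, above 5; ALP and GGT up to 2, above 2 to 3, above 3; total bilirubin up to 1.5, above 1.5 to 2, above 2;
- (b) at 2 x or more and at 3 x or more of own Baseline, and also above ULN;
- (c) with ALT or AST above 3 x ULN and total bilirubin above 2 x ULN on the same date, where this was not already met at Baseline.

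Present it for samples before the first atorvastatin dose and for the whole double-blind phase. A Week 4 sample drawn before that dose belongs to the first period, as do all samples of a subject who never starts atorvastatin. The denominator is subjects with a Baseline and at least one post-Baseline value in the period. The bands are proposed reporting categories, to be fixed before database lock; they imply no change in patient management.

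Cost: SAP wording and one table from central laboratory data already held, with no new visits or samples. With the example bands it has 5 x 2 x 3 = 30 band rows, 5 x 2 = 10 Baseline-multiple rows and 1 combined row, 41 per period. Cells will be sparse, averaging 20/(2 x 3) = 3.3 subjects per band cell.
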